ClinicalTrials.gov Protocol Registration and Results System (PRS) Receipt
Release Date: October 19, 2020

ClinicalTrials.gov ID: [Not yet assigned]

Study Identification

Unique Protocol ID: CMUH109-REC2-131

Brief Title: The Effectiveness of Acupressure for Managing Postoperative Pain and Anxiety in Patients With Thoracoscopic Surgery.

Official Title: Professor, School of Nursing, China Medical University Hospital, Principal Investigator.

Secondary IDs:

Study Status

Record Verification: October 2020

Overall Status: Recruiting

Study Start: September 20, 2020 [Actual]

Primary Completion: August 2021 [Anticipated]

Study Completion: September 2021 [Anticipated]

Sponsor/Collaborators

Sponsor: [name]

Responsible Party: Sponsor-Investigator

Investigator: [name] [[name]]

Official Title: Professor, School of Nursing

Affiliation: China Medical University Hospital

Collaborators: China Medical University Hospital

Oversight

U.S. FDA-regulated Drug: No

U.S. FDA-regulated Device: No

U.S. FDA IND/IDE: No

Human Subjects Review: Board Status: Approved

Approval Number: CMUH109-REC2-131

Board Name: Research Ethics Committee China Medical University and Hospital, Taichung, Taiwan

Board Affiliation: China Medical University and Hospital

[contact]

Email:

Address:

Study Description

Brief Summary: The purpose of this study is to explore the effectiveness of acupressure for managing postoperative pain, anxiety, analgesia consumption, early ambulation, and comfort in patients with thoracoscopic surgery.

Detailed Description: Thoracoscopic surgery is the surgical used to removal of a section or a segment of a lung lobe. One US national survey reported that 80% of patients undergoing pulmonary surgery experienced acute pain. 75-86% of these patients pointed out that experienced moderate, severe, or extreme pain, especially, on the 1st day after thoracoscopic surgery. However, inappropriate pain management after surgery is associated with limited the healing process, increased workload of heart, prolonged pulmonary rehabilitation, and increased medical costs, and can be a prediction of developing chronic pain. Acupressure is a nonpharmacological treatment for the management of postoperative pain. Recent studies have found that the application of acupressure is effective in decreasing operative pain intensity, morphine related side effects, and opioid consumptions after surgery. However, there was no further research about the role of acupressure applied to thoracoscopic surgery.

Conditions

Conditions: Lung Diseases

Keywords: acupressure
thoracoscopic surgery
acute pain
anxiety
comfort

Study Design

Study Type: Interventional

Primary Purpose: Supportive Care

Study Phase: N/A

Interventional Study Model: Parallel Assignment

Number of Arms: 2

Masking: Single (Participant)

Allocation: Randomized

Enrollment: 200 [Anticipated]

Arms and Interventions

| Arms | Assigned Interventions |
|---|--|
| Experimental: acupressure After recruitment, participants will be randomized to receive acupressure or control group. In the | acupressure The acupressure involves the " Vaccaria Semen" within skin-colored adhesive tape that placed on |

| Arms | Assigned Interventions |
|--|---|
| acupressure group, participants will receive acupressure treatment. | the "Neiguan" and "Shenmen" acupoints as an intervention measure. Continue to massage the acupoints with fingertips for 10 minutes, 3 times per day (8 and 12 in the morning, and 4 in the afternoon). The adhesive tape will be retained in situ for 2 days. |
| No Intervention: routine care After recruitment, participants will be randomized to receive acupressure or control group. In the control group, participants will receive routine care, including routine pain control. | |

Outcome Measures

Primary Outcome Measure:

1. Pain: Changes from baseline pain scale at post-operative day 2, after intervention. as assessed by Visual Analogue Scale-Pain (VAS-P). The VAS#P scale is comprised of a horizontal line 100mm long with the indication "no pain" to the left and "worst possible pain" to the right. possible scores varied between 0–100. A higher scores mean a worse outcome.

[Time Frame: Measure at before operation day, 7 post meridiem (PM), before operation; post-operative day1, 8 ante meridiem (AM), before intervention; post-operative day 1, 5 PM, after intervention; and post-operative day 2, 5 PM, after intervention]

Secondary Outcome Measure:

2. Anxiety as assessed by Visual Analogue Scale-Anxiety(VAS-A). The VAS#A scale is comprised of a horizontal line 100mm long with the indication "no anxiety" to the left and "worst possible anxiety" to the right. possible scores varied between 0–100. A higher scores mean a worse outcome.

[Time Frame: Measure at before operation day, 7 post meridiem (PM), before operation; post-operative day1, 9 ante meridiem (AM), before intervention; post-operative day 1, 5 PM, after intervention; and post-operative day 2, 5 PM, after intervention.]

3. Anxiety as assessed by State-Trait Anxiety Inventory (STAI) Y form (STAI-Y1). It is 20 questions, which were rated from 1–4. Possible scores varied between 20–80. A STAI-Y1 score>40 as evidence of a state of anxiety.

[Time Frame: Time Frame: Measure at before operation day, 7 post meridiem (PM), before operation; post-operative day1, 8 ante meridiem (AM), before intervention; and post-operative day 2, post meridiem (PM), after intervention.]

Other Pre-specified Outcome Measures:

4. Analgesia Consumption
Injection time of morphine and ketorolac would be recorded.

[Time Frame: during the whole admission, an average of 4 day.]

5. Comfort as assessed by Shortened General Comfort Questionnaire

[Time Frame: Measure at before operation day,7 post meridiem (PM), before operation; post-operative day 1, 8 ante meridiem (AM), before intervention; and post-operative day 2, 5pm, after intervention]

6. Heart rate variability as assessed by Nexus-10, wireless Biofeedback/Neurofeedback system

[Time Frame: Measure at before operation day, 7 post meridiem (PM), before operation; post-operative day1, 8 ante meridiem (PM), before intervention; post-operative day 1, 5 post meridiem (PM), after intervention; and post-operative day 2, 5 PM, after intervention.]

7. Early ambulation
The first ambulation time: act to walk with or without any kind of assistant after operation.

Eligibility

Minimum Age: 20 Years

Maximum Age:

Sex: All

Gender Based:

Accepts Healthy Volunteers: Yes

Criteria: Inclusion Criteria:

- pulmonary lung disease and will be scheduled to undergo a thoracoscopic wedge resection, segmentectomy, or lobectomy.
- American Society of Anesthesiologist physical status of Classes I-II,
- both forearms without missing limbs or arteriovenous fistula
- ability to communicate in Taiwanese or Chinese, and
- agreement to participate in this study.

Exclusion Criteria:

- diagnosed as malignant neoplasm with lung meta,
- Had a stroke or peripheral vascular disease
- Platelet count less than $20 \times 10^3/\text{mm}^3$
- Using the patient controlled analgesia, and
- any known mental illness or memory dysfunction.

Contacts/Locations

Central Contact Person: [name]

[contact] [name]

Email: [contact]

Central Contact Backup: [name]

Study Officials: [name]

Study Principal Investigator

China Medical University, China

Locations: **Taiwan**

China Medical University

[Recruiting]

Taichung, Taiwan, 40447

Contact: [name], PHD [name]

[contact]

Contact: [name], PHD [name] [contact]

Principal Investigator: [name]

Sub-Investigator: [name]

IPDSharing

Plan to Share IPD: No

References

Citations: **[Study Results]** Abouarab AA, Rahouma M, Kamel M, Ghaly G, Mohamed A. Single Versus Multi-Incisional Video-Assisted Thoracic Surgery: A Systematic Review and Meta-analysis. *J Laparoendosc Adv Surg Tech A*. 2018 Feb;28(2):174-185. doi: 10.1089/lap.2017.0446. Epub 2017 Nov 6. Review. PubMed 29106318

Amico, T. A. D. (2007). Thoracoscopic Lobectomy. *Journal of Medical Sciences*, 27(3), 95-100. [https://doi.org/10.6136/JMS.2007.27\(3\).095](https://doi.org/10.6136/JMS.2007.27(3).095)

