Description American Society of Anesthesiologists Physical Status Classification System.

Available IPD/Information:

U.S. National Library of Medicine | U.S. National Institutes of Health | U.S. Department of Health & Human Services

Official title: China Medical University Hospital

NCT number: NCT04595253

Title: The Effectiveness of Acupressure for Managing Postoperative Pain and Anxiety in Patients With Thoracoscopic Surgery

Statistical Analysis Plan

SPSS statistical software was used for data analysis, independent t test and chi-square test were used for descriptive analysis. A mixed model with repeated analysis was used to examine the effect of acupressure on pain, anxiety, and comfort. Regression analysis was to explore the influences of pain, anxiety, and comfort for study patients with thoracoscopic Surgery.

Primary Completion Date

The patient experienced moderate pain and anxiety after thoracoscopic surgery. There was no significant difference in demographic characteristics between the two groups before they received surgery. The experimental group, compared with the control group, pain intensity ($p<0.01$) and anxiety score ($p<0.05$) were statistically significant lower on day 1 and day 2 after intervention. The STAI-Y1 score ($F=2.514$, $p=.086$) and comfort level ($F=2.953$, $p=.057$) were no significant differences after intervention between two groups. The longer intervention, the significantly decreased pain intensity ($p<0.05$) for surgical procedures with lighter pain perception.

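### Participant masking is registered, but the comparator is routine care with no sham, so the self-rated outcomes cannot be read as blinded

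*Combined protocol and SAP*

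**What the plan says.** The registration record (Study Design) gives the masking as "Masking: Single (Participant", with no other role masked. The Arms and Interventions table then describes two visibly different experiences:

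- **Acupressure arm:** Vaccaria seeds under skin-coloured tape on the Neiguan and Shenmen points, kept on for 2 days, with the instruction "Continue to massage the acupoints with fingertips for 10 minutes, 3 times per day". The record does not say who does the massage.
- **Comparator:** headed "No Intervention: routine care", with the explanation "In the control group, participants will receive routine care, including routine pain control". Its intervention cell is empty.

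The primary outcome is VAS-P, defined as "Changes from baseline pain scale at post-operative day 2, after intervention". The secondary outcomes are VAS-A and STAI-Y1, and comfort is a questionnaire listed among the other pre-specified outcomes. The SAP does not mention masking. On analysis it says: "A mixed model with repeated analysis was used to examine the effect of acupressure on pain, anxiety, and comfort".

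The results text under the heading Primary Completion Date reports for the acupressure arm that "pain intensity ($p<0.01$) and anxiety score ($p<0.05$) were statistically significant lower on day 1 and day 2 after intervention". It adds: "The STAI-Y1 score ($F=2.514$, $p=.086$) and comfort level ($F=2.953$, $p=.057$) were no significant differences after intervention between two groups".

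**The concern.** The masking entry is the only statement in the documents that participants were blinded, and the arm descriptions do not support it. The role registered as masked is also the role that produces the primary and both secondary outcomes, and no masking of assessors or care providers is registered to offset this.

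A reader who trusts the entry would largely discount expectation and attention as explanations for the lower pain and anxiety scores. If participants knew their arm, those explanations remain open, and the comparison measures the whole package of tape, massage, attention and expectation against routine care. It does not isolate an effect of pressing these two points.

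**Working it through.** **1. Is the registered masking consistent with the arms?**

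| Feature | Acupressure | Routine care |
|---|---|---|
| Tape and seed on the body | Yes, 2 days | None described |
| Massage of the points | 10 min, 3 times a day | None described |
| Sham points, placebo tape or attention control | – | None described |

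The skin-coloured tape appears in one arm only, so it cannot hide the arm from its wearer. The only mention of a sham is in the title of a cited knee-replacement study in the reference list, which is not part of this design.

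The contrast in exposure is not subtle. If sessions start at 8 AM on day 1 and follow the stated times (8, 12 and 4 o'clock), the acupressure arm has had 3 × 10 = 30 minutes of massage by the day 1, 5 PM assessment. By day 2, 5 PM it has had 6 × 10 = 60 minutes.

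**2. Who rates the outcomes?** The documents do not use the word self-reported. It follows from the instruments: two visual analogue scales, a 20-item anxiety inventory and a comfort questionnaire. Heart rate variability is recorded by a device. Analgesic injections and first ambulation are recorded events.

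**3. How much could a reporting shift matter?** The documents give no figure to reproduce here. The only usable input is the total enrolment of 200. Allocation ratio, SD, alpha and power are not stated, so everything else below is an assumption.

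Assumptions: 100 per arm, VAS SD 20 or 25 mm, true effect zero, knowledge of the arm shifts the reported score by 5 mm (0.25 or 0.20 SD), normal approximation, two-sided test.

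P(p < α) = P(|Z + 5/SE| > z), with z = 1.96 for α = 0.05 and 2.576 for α = 0.01.

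*Day 2 scores:* SE = SD × √(2/100).

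| SD | SE | p<0.05 | p<0.01 |
|---|---|---|---|
| 20 | 2.83 | 42.4% | 21.0% |
| 25 | 3.54 | 29.3% | 12.3% |

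*Change from baseline,* with within-patient correlation r: SE = SD × √(2(1−r)) × √(2/100).

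| SD | r | SE | p<0.05 |
|---|---|---|---|
| 20 | 0.3 | 3.35 | 32.1% |
| 20 | 0.5 | 2.83 | 42.4% |
| 20 | 0.7 | 2.19 | 62.6% |
| 25 | 0.3 | 4.18 | 22.3% |
| 25 | 0.5 | 3.54 | 29.3% |
| 25 | 0.7 | 2.74 | 44.7% |

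*Unequal allocation, 80:120, day 2 scores:* SE = SD × √(1/80 + 1/120) = 2.89 or 3.61, giving 41.0% or 28.3% at 0.05.

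*Other shift sizes, in SD units, 100 per arm, single time point:* shifts of 0.1, 0.2, 0.3, 0.4 and 0.5 SD give about 11%, 29%, 56%, 81% and 94%, against 5% with no shift.

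**The case against.** **Limited disclosure.** Participants may have been masked to the hypothesis, or not told what the other arm received. That would normally be described in the consent form, which is not in the text reviewed. This stands as a reason to let the sponsor document it. It does not support the entry as it is, because nothing in the protocol or SAP describes such a method.

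**The entry may have changed.** The record is a receipt from October 2020, before a trial number was assigned, and the SAP page was written later. This also stands: the current entry should be checked first.

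**The design is legitimate and the harm unproven.** A routine-care comparator suits an effectiveness question, the results text already speaks of experimental versus control group, and no estimate changes. All true. The point is not that a sham was required, but that the record claims a protection the described design does not provide, on the outcomes that matter most.

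**Not every self-rated outcome differed.** STAI-Y1 (p=.086) and comfort (p=.057) did not reach significance. This says little either way: the text does not state which effect each F statistic tests, and non-significance on some scales does not establish masking.

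**The figures are hypothetical.** Agreed. They use a two-group z-test where the SAP names a repeated-measures mixed model, and the size of the shift is assumed. The conclusion does not rest on them.

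**The massage minutes are not needed.** They assume full adherence and a first session at 8 AM on day 1. The outcome list places the pre-intervention VAS-A at 9 AM on day 1, after the 8 AM session, and those entries need reconciling separately. The tape alone already distinguishes the arms.

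**Conclusion.** The concern holds. Participant masking is not a property of the design as described, and VAS-P, VAS-A, STAI-Y1 and comfort should be read as unblinded self-report. That finding comes from comparing the masking entry with the arm descriptions and needs no numerical assumption.

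Bias is possible but not shown, and the documents do not allow its size to be estimated. Under the stated assumptions, a 5 mm reporting shift with no true effect would give p<0.05 in 29–42% of trials on day 2 scores and in 22–63% on change from baseline. It would give p<0.01 in 12–21% on day 2 scores. A reporting shift of modest size therefore cannot be dismissed as an explanation on the strength of the p-values alone.

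**What to change.** 1. Check the current registry entry. If it is unchanged, set masking to None (Open Label), unless the sponsor can document how participants were masked and to what.
2. State the contrast as acupressure as delivered, including expectation and any attention, versus routine care, and limit the conclusion to that.
3. Name the lack of participant blinding of self-reported outcomes as a limitation wherever the pain and anxiety results are given.
4. Optional: if heart rate variability, analgesic injections or first ambulation are shown beside the VAS results, specify their analysis first and label it post hoc, because the SAP names no model for them. Heart rate variability is the least open to reporting bias, being measured by a device. Injections and ambulation can still be influenced by patient and staff behaviour.

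Items 1–3 cost one registry field, one limitation statement and a narrower conclusion, with no change to the VAS estimates or p-values. Item 4 needs a short added specification. The downside is that the stated design looks weaker and the claim is smaller.

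### Analgesia consumption is a stated aim, but the plan records only an undefined injection time, specifies no amount, and the SAP does not analyse it

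*Combined protocol and SAP*

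**What the plan says.** The Brief Summary gives the purpose as exploring the "effectiveness of acupressure for managing postoperative pain, anxiety, analgesia consumption, early ambulation, and comfort in patients with thoracoscopic surgery". The Detailed Description supports this with earlier work in which acupressure was effective in "decreasing operative pain intensity, morphine related side effects, and opioid consumptions after surgery".

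Consumption is made operational in one place only, item 4 under "Other Pre-specified Outcome Measures". The variable is: "Injection time of morphine and ketorolac would be recorded". The time frame is "during the whole admission, an average of 4 day". No mg, unit, total, count definition or rule for summarising the two drugs is given.

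Two other entries bear on the point. The control arm description says that "participants will receive routine care, including routine pain control", with no amount per injection stated. Patient-controlled analgesia is an exclusion criterion, so the recorded drugs are given as discrete injections.

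The Statistical Analysis Plan applies a mixed model to pain, anxiety and comfort, and a regression to the same three. It does not mention analgesia consumption, and neither does the summary of results that follows it.

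**The concern.** An aim about consumption needs a variable that measures how much was consumed. The plan names a variable, but it is not a quantity of drug on any natural reading, and the SAP does not turn it into one. As written, the aim has no defined endpoint and no planned comparison between arms.

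A reduction in opioid use is part of the case for the intervention. If it occurs through smaller amounts at each injection, neither times nor counts will show it. The record would also help in reading the primary outcome: VAS-P is taken at 5 PM on postoperative days 1 and 2, and patients in either arm may have had morphine or ketorolac beforehand. Knowing how much of each drug preceded each reading helps to interpret a pain difference, or the lack of one.

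**Working it through.** The plan gives no figure for this outcome, so there is nothing to reproduce. The check has two parts.

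**1. What each reading of the variable can recover**

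| Reading of injection time | Number of injections | Amount |
|---|---|---|
| Clock time of every injection, by drug | yes | no |
| Number of injections, by drug | yes | only if every injection of a drug is the same size |
| Time to first injection | no | no |

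The documents do not say which reading is meant or that amounts are constant.

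Hand examples with assumed values:
- Constant amount, 4 against 3 morphine injections: 1 − 3/4 = 25% lower by count and 25% lower by amount. Sparing is visible.
- Equal counts, 4 against 4, amount per injection 0% to 50% lower in one arm: the count differs by 0%, consumption by 0% to 50%. Sparing is missed.
- 3 morphine + 1 ketorolac against 1 morphine + 3 ketorolac: 4 against 4 if the drugs are summed, but 3 against 1 for morphine alone (1 − 1/3 = 67% lower). Sparing is missed only if the drugs are summed.

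**2. Size**

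From the documents: 200 enrolled, two arms. Assumed: equal split (100 per arm), two-sided 5% test, morphine injections per patient Poisson with mean 2, amount per injection independent with CV 40%, control mean amount set to 1. The variance of a patient's total is then mean count × (mean amount)² × (1 + 0.4²), and power is approximately Φ(z − 1.96) with z = difference / SE.

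*Smaller amount per injection, same count.* The count has the same distribution in both arms, so its rejection rate is the nominal 5% (simulated 0.045 to 0.058). For total mg with a proportional reduction d:

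difference = 2d; SE = √{2 × 1.16 × [1 + (1 − d)²] / 100}

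| d | Difference | SE | z | Power, mg | Power, count |
|---|---|---|---|---|---|
| 10% | 0.20 | 0.205 | 0.98 | about 16% | 5% |
| 25% | 0.50 | 0.190 | 2.63 | about 75% | 5% |
| 50% | 1.00 | 0.170 | 5.87 | above 99% | 5% |

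Simulation at d = 25% gave 0.752. If only 50 per arm were analysed, SE = √(3.625/50) = 0.269, z = 1.86 and power is about 46% (simulated 0.473).

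*Fewer injections, same amount each.* With 25% fewer morphine injections (2 against 1.5):
- Count: SE = √(3.5/100) = 0.187, z = 0.5/0.187 = 2.67, power about 76%.
- Total mg: SE = √(3.5 × 1.16/100) = 0.2015, z = 0.5/0.2015 = 2.48, power about 70%.

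A per-drug count loses nothing here. The loss is specific to changes in amount per injection.

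**The case against.** The strongest reply is that the wording is loose but the data may be adequate. Both drugs are named and nothing says they are added together, so a log by drug would give morphine counts directly. With patient-controlled analgesia excluded, such a count is a reasonable coarse proxy, and the calculation above shows that it detects fewer injections at least as well as mg. Logged times would also show which drug preceded each 5 PM reading, and a randomised VAS-P comparison under routine pain control is interpretable as an effect under usual care. The outcome is neither primary nor secondary.

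All of that stands. A reader might infer that the consumption aim cannot be answered at all, or that opioid sparing would be invisible. The documents do not support this: it would require that the drugs are summed, or that only the first injection is timed, and they state neither. For the same reason, a simulation in which a summed count misses a switch from morphine to ketorolac (5% power against 77% for morphine alone) shows the effect of an assumed summing rule, not of the plan.

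The reply does not remove the defect. The proxy works only if every injection is logged, the drugs are summarised separately and amounts per injection do not differ between arms. The plan commits to none of these, and the SAP has no analysis through which the proxy would be used.

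**Conclusion.** The point holds in this limited form: consumption is a stated purpose without an operational measure of amount, without a stated separate summary for the opioid and the non-opioid, and without an analysis. Opioid sparing may be missed; it would not necessarily be. The certain blind spot is a difference in amount per injection, where a count stays at about 5% power while total mg has about 75% for a 25% reduction (about 16% for 10%, above 99% for 50%). These figures rest on the assumed equal allocation, injection mean and CV, none of which is in the documents. The 5% for the count does not depend on the size of the reduction.

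The time frame adds a second weakness. A whole-admission total grows with length of stay, which varies between patients, so arms could differ in total for reasons other than analgesic need per day.

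The change should be made, but the primary pain comparison does not depend on it.

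**What to change.** Redefine outcome 4: for each injection, record the drug, the amount in mg and the clock time. Report cumulative morphine mg and cumulative ketorolac mg separately, as between-arm differences with 95% CIs, over a common fixed window, for example from end of surgery to the 5 PM readings on postoperative days 1 and 2. Those cut-offs match the VAS-P readings, so the same tables show how much of each drug preceded each score. Keep the whole-admission total and the injection counts by drug as descriptive items. Add this analysis to the SAP, which at present has none for this outcome.

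The cost is a little more data entry per injection. This assumes that the amounts are in the medication record; the documents name no data source. If they are, the amounts can also be abstracted for patients already treated. The change concerns data capture and analysis only and leaves clinical dosing as it is.

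### Three resections are pooled and the mixed model specifies no procedure term: a modest, cheaply recovered loss of precision, not a bias

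*Combined protocol and SAP*

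**What the plan says.** The inclusion criteria (Eligibility) admit patients "scheduled to undergo a thoracoscopic wedge resection, segmentectomy, or lobectomy". The expected mix of the three is not given.

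Under Study Design the allocation entry reads "Allocation: Randomized". Arms and Interventions adds only that "participants will be randomized to receive acupressure or control group". No ratio, blocking, stratification factor or minimisation is described. Anticipated enrolment is 200.

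The Statistical Analysis Plan describes the efficacy model in one sentence: "A mixed model with repeated analysis was used to examine the effect of acupressure on pain, anxiety, and comfort". It lists no fixed effects or covariates. The next sentence adds a second model: "Regression analysis was to explore the influences of pain, anxiety, and comfort for study patients with thoracoscopic Surgery". Its predictors are not listed either.

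The results text under the Primary Completion Date heading makes one statement about balance: "There was no significant difference in demographic characteristics between the two groups before they received surgery". Procedure by arm is not mentioned. The same paragraph ends with a pain finding "for surgical procedures with lighter pain perception".

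**The concern.** The primary outcome is change in VAS pain (0 to 100 mm) at post-operative day 2. The amount of lung removed is a plausible cause of that score whatever the treatment, and the results text itself links pain to procedure. A variable of that kind, known before the first acupressure session, should have a stated role in the analysis. Here it has none: the reader cannot tell whether procedure was a covariate, a subgroup or an exploratory predictor.

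Two things are at stake:

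- **Precision.** Pain variation between procedures stays in the residual, and if one arm happens to receive more of the less painful resections, that trial's estimate shifts accordingly.
- **Transparency.** With no role fixed, an unadjusted, an adjusted or a procedure-specific result could each be presented after the data are seen.

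**Working it through.** **The plan's own figure.** Enrolment of 200 comes with no alpha, power, SD, target difference or dropout rate, so it cannot be reproduced. For scale only, with an assumed 100 per arm and two-sided alpha of 0.05, the difference detectable with 80% power is (1.960 + 0.842) × √(2/100) = 0.396 SD.

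**Inputs.** Only the total of 200 comes from the documents. Assumed: 1:1 allocation; one third of patients having lobectomy; a between-procedure pain difference d of 5, 10 or 15 mm; SD 22 mm. The direction of the difference is also assumed. The number analysed is not reported, so 50 per arm is shown as well.

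**Step 1: chance imbalance.** Procedure is collapsed here to lobectomy against the rest. The SD of the difference between arms in lobectomy share is √(2 × 1/3 × 2/3 ÷ n).

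- n = 100 per arm: √(0.444/100) = 0.067; 95% range ±1.96 × 0.067 = ±13 percentage points.
- n = 50 per arm: √(0.444/50) = 0.094; 95% range ±18 percentage points.

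**Step 2: resulting shift in the arm difference** (1.96 × SD of imbalance × d).

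| d | 100 per arm | 50 per arm |
|---|---|---|
| 5 mm | 0.7 mm | 0.9 mm |
| 10 mm | 1.3 mm | 1.8 mm |
| 15 mm | 2.0 mm | 2.8 mm |

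For comparison, the unadjusted standard error at 100 per arm is 22 × √(2/100) = 3.1 mm, with a 95% half-width of 6.1 mm. That interval already includes the variation in the table.

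**Step 3: precision recovered.** With three equally frequent procedures at 0, d/2 and d, the between-procedure variance is d²/6. Its share of total variance is R² = (d²/6)/22², and the standard error falls by 1 − √(1 − R²).

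- d = 5: 4.17/484 = 0.009; reduction 0.4%.
- d = 10: 16.7/484 = 0.034; reduction 1.7%.
- d = 15: 37.5/484 = 0.077; reduction 4.0%.

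**Step 4: a wider range.** With two procedure classes, a share of 0.3 to 0.5 in the more painful class, SD 20 to 25 mm and d of 5 to 20 mm, power of 80% without the term becomes 80.3% (SD 25, share 0.3, d 5) to 89.9% (SD 20, share 0.5, d 20). If d is at most 15 mm the upper figure is 85.6%. At SD 25, share 0.5 and d 10, the standard error goes from 3.54 to 3.46 mm and power from 80.0% to 81.6%.

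**Step 5: validity.** 40,000 trials with no acupressure effect were simulated in each of three settings (share, d, SD: 0.5, 10, 25; 0.5, 15, 25; 0.3, 15, 20). The mean estimate was within 0.03 mm of zero with and without the procedure term. Type I error was 4.9 to 5.2% without it and 4.9 to 5.3% with it.

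**Step 6: which baseline.** Suppose a procedure adds a constant d to every post-operative score. Subtracting the pre-operative score leaves d in the change; subtracting the post-operative day 1 8 AM score, taken after surgery and before acupressure, cancels it. The plan does not say which score the model uses as baseline.

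**The case against.** The strongest reply is that an unstratified, unadjusted randomised comparison is valid, and that the quantities above are small. This stands. Three inferences that a reader might draw go further than the documents allow.

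- **That the model had no procedure term.** The Statistical Analysis Plan lists no terms of any kind: not group, time, their interaction or baseline. The results sentence on procedures suggests that procedure entered some analysis. What can be said is that no procedure term is specified.
- **That the documents rank the three resections by pain.** The results sentence names no procedure and gives no size. That lobectomy hurts more, and by how much, is an assumption here.
- **That procedure imbalance makes the acupressure effect spurious.** Randomisation needs comparable arms, not identical patients. An omitted prognostic factor in a linear model causes no average bias and leaves type I error at its nominal level, as Step 5 shows. One trial's realised imbalance does move its estimate, but the unadjusted standard error already allows for that.

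It is also fair to say that controls are not untreated: they receive routine care including routine pain control. And the day 1 8 AM score, if used in the model, would absorb part of any procedure effect. Finally, the Statistical Analysis Plan is in the past tense and sits beside results, so promoting a newly adjusted estimate to the main result now would be a post hoc change of primary model. That limits the remedy.

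None of this removes the core: a variable that the document links to pain, known for each patient before the intervention, has no stated place in the model.

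**Conclusion.** The point holds as a low-cost improvement, not as an error that undermines the comparison. On the assumed inputs, chance imbalance in procedure is worth 0.7 to 2.0 mm at the 95% limit with 100 per arm, against a confidence half-width of about 6 mm. Adjustment reduces the standard error by about 2 to 4% when procedures differ by 10 to 15 mm, and by under 1% at 5 mm. The gain is smaller still if the day 1 8 AM score is in the model, and larger only if procedures differ by more than assumed or the SD is lower.

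The procedure mix, SD and between-procedure differences are not in the documents; the sponsor can replace them with trial data. The part that does not depend on them is the reporting gap: the model terms, the procedure distribution by arm and the status of the procedure-specific pain finding are all unstated.

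**What to change.** 1. In the Statistical Analysis Plan, list the terms of the mixed model for pain, anxiety and comfort. Include scheduled procedure (wedge resection, segmentectomy, lobectomy) as a fixed effect, and say which score serves as baseline. Use scheduled rather than performed procedure because the inclusion criterion fixes it before the intervention.
2. Tabulate scheduled and performed procedure by arm beside the demographic comparison.
3. Because results are already reported, present a procedure-adjusted estimate added now as a post hoc sensitivity analysis next to the result of the model as it was run. If procedure was already in that model, say so.
4. State whether the pain finding for procedures with lighter pain was pre-specified, which procedures it covers and which model produced it.

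The cost is one clause in the plan, one table, one rerun of the model and two degrees of freedom. Eligibility depends on the scheduled procedure, so it should already be held for every patient.
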